10.3. Criteria for Potentially Clinically Significant Values (PCSV)

| Creatinine (CREAT) | >=30% increase from individual subject baseline >=60% increase from individual subject baseline | Benichou C., 1994. 2 independent criteria |
|--|--|--|
| Urate (URATE) Hyperuricemia Hypouricemia | >=30% increase from individual subject baseline >=60% increase from individual subject baseline | Harrison- Principles of internal Medicine 17th Ed., 2008. Two independent criteria |
| Urea Nitrogen (UREAN) | >=30% increase from individual subject baseline >=60% increase from individual subject baseline | |
| Chloride (CL) Hypochloremia Hyperchloremia | <80 mmol/L and baseline \ge 80 mmol/L >115 mmol/L and baseline \le 115 mmol/L | Two independent criteria |
| Sodium (SODIUM) Hyponatremia Hypernatremia | <129 mmol/L and baseline ≥129 mmol/L >150 mmol/L and baseline ≤ 150 mmol/L | Two independent criteria |
| Potassium (K) Hypokalemia Hyperkalemia | <3.5 mmol/L and baseline \ge 3.5 mmol/L >5.0 mmol/L and baseline \le 5.0 mmol/L | FDA Feb 2005. Two independent criteria |
| Cholesterol (Cholesterol) | >6.20 mmol/L and \leq 6.20 mmol/L at baseline | |
| Triglycerides (TRIG) | > 5.64 mmol/L and ≤ 5.64 mmol/L at baseline | Threshold for therapeutic intervention with pharmacotherapy in children. (Expert Panel on Integrated Guidelines for Cardiovascular Health and Risk Reduction in Children and Adolescents; 2011). CF = g x 1.14 = mmol |
| Glucose (GLUC) Hypoglycaemia Hyperglycaemia | ≤ 2.7 mmol/L ≥10 mmol/L | |
| Albumin (ALB) | <25 g/L and ≥ 25 g/L at baseline | |
| Calcium (CA) | <2 mmol/L and baseline ≥2 mmol/L >2.9 mmol/L and baseline ≤2.9 mmol/L | |

| LDL Cholesterol (LDL) | >4.91 mmol/Land ≤4.91 mmol/L at baseline | Threshold for therapeutic intervention with pharmacotherapy in children (Expert Panel on Integrated Guidelines for Cardiovascular Health and Risk Reduction in Children and Adolescents; 2011). |
|-----------------------------------|---|---|
| Hematology | | |
| Leukocytes (WBC) | <4.0 Giga/L and ≥4.0 Giga/L at baseline >13.5 Giga/L and ≤13.5 Giga/L at baseline | |
| Lymphocytes (LYM) | <0.6 Giga/L and ≥0.6 Giga/L at baseline >6.0 Giga/L and ≤6.0 Giga/L at baseline | |
| Neutrophils (NEUT) | <1.2 Giga/L and ≥1.2 Giga/L at baseline >ULN and baseline ≤ ULN | |
| Monocytes (MONO) | >1.2 Giga/L and \leq 1.2 Giga/L at baseline | |
| Basophils (BASO) | >0.2 Giga/L | |
| Eosinophils (EOS) | (>0.5 Giga/L and >ULN) and (\leq 0.5 Giga/L or \leq ULN at baseline) | Harrison- Principles of internal Medicine 17th Ed., 2008. |
| Hemoglobin (HGB) | ${<}100$ g/L and ${\geq}100$ g/L at baseline or any decrease ${\geq}~20$ g/L | Two criteria are independent |
| | >200 g/L and \leq 200 g/L at baseline | |
| Hematocrit (HCT) | $<0.37 \text{ v/v} \text{ and } \ge 0.37 \text{ v/v} \text{ at baseline for Male;}$ | Two criteria are independent |
| | $<0.33 \text{ v/v}$ and $\ge 0.33 \text{ v/v}$ at baseline for Female | |
| | >0.52 v/v and ≤0.52 v/v at baseline for Male; >0.47 v/v and ≤0.47 v/v at baseline for Female | |
| Platelets (PLAT) | <100 Giga/L and ≥100 Giga/L at baseline >700 Giga/L and ≤700 Giga/L at baseline | International Consensus meeting on drug- induced blood cytopenias, 1991. Two independent criteria |
| Urinalysis | | |
| pH (PH) | <5 or >7 | |
| Ketones (KETONES) Ketonuria | Presence and absence at baseline | Semi-quantitative methods |
| Ketonuna | | |

| Glucose (GLUC) Glycosuria | Presence and absence at baseline | Semi-quantitative methods |
|---|--|---|
| Erythrocytes (RBC) Microscopic Hematuria | > 5 RBCs/ HPF and ≤5 RBCs/ HPF at baseline | Semi-quantitative methods |
| Protein (PROT) Proteinuria | \geq 1+ and <1 at baseline | Semi-quantitative methods, $\geq 1+$ means concentration ≥ 30 mg/dL |
| Vital Signs | | |
| HR | ≤50 bpm and decrease from baseline ≥20 bpm ≥120 bpm and increase from baseline≥20 bpm | To be applied for all positions (including missing) except STANDING. |
| SBP | ≤90 mmHg and decrease from baseline ≥20mmHg ≥119 mmHg and increase from baseline ≥20 mmHg. | |
| DBP | ≤54 mmHg and decrease from baseline ≥10 mmHg ≥78 mmHg and increase from baseline ≥10 mmHg | |
| Temperature | Rectal, Tympanic: >100.4 °F/38.0 °C Oral: >99.5 °F/37.5 °C Axillary or skink infrared (temporal): >37.2 °C | |
| Respiratory rate | < 12 per minute and ≥12 per minute at baseline >20 per minute and ≤20 per minute at baseline | |
| Weight | ≥5 % weight loss from baseline ≥5 % weight gain from baseline | Based on identification of trends in the child's growth with a series of visits WHO Multicentre Reference Study Group, 2006; Center for Disease Control. Growth chart 2007. |

10.4. Search Criteria for TEAE of Special Interest for Dupilumab

| AESI | Search Criteria |
|--|--|
| Anaphylactic reactions | SMQ narrow "Anaphylactic Reactions" |
| Systemic or severe hypersensitivity reactions | Hypersensitivity: Narrow SMQ for hypersensitivity excluding preferred term equal to dermatitis atopic or eczema Note: manual adjudication of relevant PTs will be required by the study medical monitor, before database lock |

CONFIDENTIAL

Page 79 of 86

| Helminthic infections ² | -HLT = Cestode infections |
|---|--|
| | -HLT = Helminthic infections NEC |
| | -HLT = Nematode infections |
| | -HLT = Trematode infections |
| Any type of conjunctivitis or blepharitis (severe or serious) | Broad CMQ conjunctivitis (Conjunctivitis, Conjunctivitis allergic, Conjunctivitis bacterial, Conjunctivitis viral, Atopic keratoconjunctivitis, Blepharitis, Dry eye, Eye irritation, Eye pruritus, Lacrimation increased, Eye discharge, Foreign body sensation in eyes, Photophobia, Ocular hyperaemia, Conjunctival hyperaemia, Xerophthalmia) |
| | Blepharitis PTs (Blepharitis, blepharitis allergic) |
| | Serious AE= "Yes" OR Severity= "severe" |
| | Note: manual adjudication of relevant PTs will be required by the study medical monitor, before database lock. |
| Keratitis | Any of the following PTs: a. Keratitis b. Allergic keratitis c. Ulcerative keratitis d. Atopic keratoconjunctivitis e. Herpes ophthalmic f. Ophthalmic herpes simplex Note: manual adjudication of relevant PTs will be required by the study |
| | medical monitor, before database lock. |

¹ The search criteria are meant to assist the process of identification of TEAE of Special Interest/TEAE Syndrome. However, since these criteria might not be exhaustive in some cases or may not be specific in other cases. Hence an additional blinded review of all PTs in the database may be performed by the Medical monitor, based on medical judgement, to identify any TEAE of Special Interest/TEAE Syndrome that might have been missed by the criteria or to identify any TEAE may been inaccurately assigned as AESI by the algorithmic search

| 10.5. | Search Criteria for TEAE of Special Interest for AR101 |
|-------|--|
| | |

| AESI | Search Criteria |
|--|--|
| Anaphylactic reactions | SMQ narrow "Anaphylactic reactions" |
| Gastrointestinal AEs resulting in prolonged disruption of dosing | Disruption of AR101 dosing ≥7 consecutive days AND Any PT under SOC "Gastrointestinal disorders" |

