10.4.3. Other Events that Require Accelerated Reporting to Sponsor

The following events also require reporting to the sponsor (or designee) within 24 hours of learning of the event:

- **Pregnancy:** Although pregnancy is not considered an AE, it is the responsibility of the investigator to report to the sponsor (or designee), within 24 hours of identification, any pregnancy occurring in a female study subject, during the study or within 12 weeks of the last dose of study drug. Any complication of pregnancy affecting a female study subject, and/or fetus and/or newborn that meets the SAE criteria must be reported as an SAE. Outcome for all pregnancies should be reported to the sponsor.
- Adverse Events of Special Interest: All AESI, serious and non-serious, must be reported within 24 hours of identification using the same reporting process as for SAE reporting, per Section 10.4.2.

Adverse events of special interest for dupilumab in this study include the following:

- Anaphylactic reactions
- Systemic or extensive hypersensitivity reactions
- Helminthic infections
- Conjunctivitis (any type or etiology), keratitis, or blepharitis (for all these AEs only events that are severe or serious or lasting \geq 4 weeks will be reported as AESIs)

Adverse events of special interest for AR101 in this study include:

- Anaphylactic reactions
- Gastrointestinal AEs resulting in prolonged disruption of dosing

Refer to the study manual for the procedures to be followed.

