4.6.2. Adverse Events of Special Interest

Adverse event of special interest (AESI) for dupilumab in this study category includes:

- Anaphylactic reactions
- Systemic or severe hypersensitivity reactions
- Helminthic infections
- Conjunctivitis (any type or etiology), keratitis, or blepharitis (for all these AEs only events that are severe or serious or lasting ≥4 weeks will be reported as AESIs)

Adverse events of special interest for AR101 in this study include:

- Anaphylactic reactions
- Gastrointestinal AEs resulting in prolonged disruption of dosing

Section 10.4 provides a list of AESIs search criteria.

Anaphylactic reactions: Anaphylaxis is defined as severe, potentially life-threatening systemic hypersensitivity reaction, characterized by being rapid in onset with life-threatening airway, breathing, or circulatory problems that is usually, though not always, associated with skin and mucosal changes.

Gastrointestinal adverse events and disruption of dosing: At each study visit, the site must solicit specific symptoms from subjects that may indicate the development of EoE. These include symptoms of both advanced and early disease such as food impaction, dysphagia, and choking or gagging with meals, gastroesophageal reflux, nausea, vomiting, and abdominal pain. Prolonged disruption of dosing is defined as withholding AR101 for >7 consecutive days and is an individual stopping rule that results in permanent discontinuation of dosing.

CONFIDENTIAL

Page 31 of 86

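### The AESI search criteria in SAP 10.4 and 10.5 do not match the AESI definitions in SAP 4.6.2 and Protocol 10.4.3, so AESI-category counts and time-to-first-AESI results can be wrong

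*SAP*

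**What the plan says.** **Eye events, definition.** SAP 4.6.2 lists conjunctivitis, keratitis and blepharitis together and applies one qualifier: "for all these AEs only events that are severe or serious or lasting ≥4 weeks will be reported as AESIs". Protocol 10.4.3 has the same rule and requires sites to report such events to the sponsor within 24 hours.

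**Eye events, search.** SAP 10.4 splits them into two rows. The first is labelled "Any type of conjunctivitis or blepharitis (severe or serious" and its filter accepts an event only if it is flagged serious or graded severe. The second, for keratitis, is a list of preferred terms (PTs) beginning "Any of the following PTs: a. Keratitis b. Allergic keratitis c. Ulcerative keratitis d. Atopic keratoconjunctivitis", with no condition on seriousness, severity or duration. Both rows carry a note that the medical monitor must adjudicate the relevant PTs before database lock. A footnote under the table says the criteria are an aid to identification, and that a further blinded review of all PTs may be done to add missed events or remove misassigned ones.

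**Gastrointestinal (GI) events.** The AR101 AESI is a GI event that results in prolonged disruption of dosing. SAP 4.6.2 says: "Prolonged disruption of dosing is defined as withholding AR101 for >7 consecutive days". Protocol 6.1.2.5 gives the same definition, and the stopping rule in Protocol 6.1.2.3 and the deviation list in SAP 10.6 also use more than 7 days. The search in SAP 10.5 reads "Disruption of AR101 dosing ≥7 consecutive days", combined with any PT in the GI system organ class (SOC). This row has no adjudication note.

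**Use.** SAP 5.7.2 summarizes AESIs by the search categories and estimates time to first AESI by category with Kaplan-Meier curves and Cox hazard ratios.

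**The concern.** The search criteria are what the programmer will run. Where they differ from the definition, the tabulated AESIs are a different set of events from the one the protocol defines and the sites report.

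The most consequential gap is the lost duration condition. Persistent but non-severe conjunctivitis or blepharitis is a kind of event the definition takes care to include, and the search cannot find it. The keratitis and GI criteria err the other way by admitting events the definition excludes. SAP 5.7.2 presents the hazard ratios as a means of detecting safety signals, so the rule for what counts as an event should be the prespecified one.

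**Working it through.** No sample size, power or alpha figure is involved, and the plan states no expected AESI rate, so there is nothing to recompute. The check sets each definition beside its search criterion and identifies the events on which they disagree.

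| Event | Definition (SAP 4.6.2; Protocol 10.4.3 and 6.1.2.5) | Search (SAP 10.4, 10.5) | Classified differently | Direction |
|---|---|---|---|---|
| Conjunctivitis, blepharitis | severe OR serious OR ≥4 weeks | severe OR serious | not severe, not serious, ≥4 weeks | missed |
| Keratitis | severe OR serious OR ≥4 weeks | PT list only | not severe, not serious, <4 weeks | added |
| GI with disruption | disruption >7 days | disruption ≥7 days AND a GI-SOC PT | exactly 7 days, with a GI-SOC PT | added |

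**Conjunctivitis and blepharitis.** The search set is the definition set without its third limb. Every event that qualifies by duration alone (4 × 7 = 28 days or more) is lost. The filter does not refer to treatment, so this can happen in either arm.

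**Keratitis.** With no qualifier, the search set contains the definition set for the listed PTs plus every short, non-serious, mild or moderate event.

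**Overlap.** Atopic keratoconjunctivitis is in both eye lists. A mild, short, non-serious case is rejected by the first row and accepted by the second. The two rows therefore cannot both be implementing the single definition.

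**GI.** The sets differ at one value, a gap of exactly 7 days, and only when a GI-SOC PT is also present. Protocol 6.1.2.2 puts 7 consecutive missed doses in the return-to-clinic band, so the protocol does not treat that gap as meeting the stopping rule.

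**Do the review steps close the gaps?** The adjudication in the eye rows is mandatory, but its stated object is which PTs are relevant. It gives no duration or severity rule. Adjudicating PTs does not restore a duration condition that the filter lacks. The footnote review could catch missed or misassigned events, but it is optional and rests on medical judgement. It also sits under the 10.4 table, and the GI row in 10.5 has no equivalent.

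**Can the definition be programmed?** Yes. The adverse event listing in SAP 5.7.1 already carries start date, end date or ongoing status, and duration. One detail is open: SAP 6.3 imputes AE end dates only as an intermediate step and does not keep them in the final dataset. A duration condition therefore needs its own rule for ongoing events and missing end dates.

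**The case against.** The strongest defence is that the criteria are declared to be an aid, that the medical monitor must adjudicate both eye rows before lock, and that no event disappears. Every eye TEAE is in the SOC/PT and severity tables of SAP 5.7.1, its duration is in the listing, and sites report under the full three-part definition. The AESI outputs are descriptive and lie outside the type I error control in SAP 5.6.3. All of this stands. It limits the consequence to the AESI-category summaries and the time-to-first-AESI results. It does not make the search agree with the definition.

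A reader might also infer more than the documents support:

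- That AESI counts are bound to be wrong. An error needs such an event to occur and adjudication or review not to correct it.
- That ocular risk is understated in the dupilumab arm specifically. The filter is the same in both arms, and the effect on the comparison between arms is unknown.
- That any brief mild keratitis will be counted. The required adjudication may remove some, though under no stated severity or duration rule.
- That every 7-day disruption becomes a false GI AESI. The criterion also requires a GI-SOC PT.
- That the GI search must require the event to precede the disruption and be its recorded reason. The search cell does join its two conditions without a link, but the row title states that the GI event results in the disruption. Action taken with AR101 and reasons for missed doses are listed (SAP 5.7.1 and 5.5.1). Neither document contains such a timing rule, so it is not asked for here.

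**Conclusion.** The mismatch is real and is plain from the text. As written, the search can miss persistent non-severe conjunctivitis and blepharitis in either arm, can admit brief mild keratitis, and can admit GI cases at exactly 7 days. The first is the substantive item. The other two are smaller and run in the opposite direction.

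The number of events affected cannot be derived. The documents give no rates for ocular events, for their duration, or for 7-day gaps, and any figure would rest on assumed rates. The conclusion assumes only that the search is programmed as SAP 10.4 and 10.5 state and that the optional review does not override it. The primary endpoint is untouched. The correction is still worth making before lock, because these are prespecified safety analyses in a pediatric trial.

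**What to change.** Before database lock, amend the SAP appendix:

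1. In the conjunctivitis/blepharitis row of SAP 10.4, add OR duration ≥28 days to the filter and change the row label to match. State how duration is derived for ongoing events and missing end dates.
2. Apply the same three-part filter (severe, serious, or ≥28 days) to the keratitis row, so that atopic keratoconjunctivitis is judged by one rule in both lists.
3. Reconcile the ≥7-day wording in SAP 10.5 with the >7-day wording in SAP 4.6.2, SAP 10.6, and Protocol 6.1.2.3 and 6.1.2.5, so that the GI search and the AESI definition use one threshold. Which value applies is for the sponsor to settle.

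The cost is appendix wording and a small programming change. No new data are needed, since AE dates, seriousness and severity are already collected.

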10.6. Important Protocol Deviations

*Note: This is a preliminary list and the final list will be generated prior to database lock.

CONFIDENTIAL

Page 80 of 86

| Category | Description of Protocol Deviation | Notes |
|-----------------------|---|-------|
| Entered study even | Male or female Aged 6 to 17 years (inclusive) | |
| though entry criteria | | |
| was not satisfied | | |
| Entered study even | Subject has a clinical history of allergy to peanuts or peanut | |
| though entry criteria | containing foods (symptom[s] of reaction due to exposure). | |
| was not satisfied | | |
| Entered study even | Experience dose-limiting symptoms at or before the 100 mg | |
| though entry criteria | challenge dose (<=144 mg cumulative) of peanut protein on | |
| was not satisfied | screening DBPCFC and not experiencing dose-limiting symptoms | |
| | to placebo or Missing | |
| Entered study even | Serum IgE to peanut of $>=24$ kUA/L and/or a SPT to peanut $>=10$ | |
| though entry criteria | mm compared to a negative control or missing value (up to PA1) | |
| was not satisfied | min compared to a negative control of missing value (up to 1711) | |
| Entered study even | Subjects/legal guardians must be trained on the proper use of the | |
| though entry criteria | epinephrine autoinjector device to be allowed to enroll in the study | |
| was not satisfied | concerning automjector device to be anowed to enroll in the study | |
| | Subjects with other known food allergies must some to aliminate | |
| Entered study even | Subjects with other known food allergies must agree to eliminate | |
| though entry criteria | these other food items from their diet so as not to confound the | |
| was not satisfied | safety and efficacy data from the study | |
| Entered study even | Willing and able to comply with all clinic visits and study-related | |
| though entry criteria | procedures | |
| was not satisfied | | |
| Entered study even | Written informed consent from parent/guardian for minor subjects | |
| though entry criteria | | |
| was not satisfied | | |
| Entered study even | Written assent from minor subjects as appropriate (e.g. above the | |
| though entry criteria | age of 6 years or the applicable age per local regulatory | |
| was not satisfied | requirements) | |
| Entered study even | Any previous exposure to marketed dupilumab or dupilumab in a | |
| though entry criteria | clinical trial | |
| was not satisfied | | |
| Entered study even | Member of the clinical site study team or his/her immediate family | |
| though entry criteria | | |
| was not satisfied | | |
| Entered study even | History of other chronic disease (other than asthma, AD, or allergic | |
| though entry criteria | rhinitis) requiring therapy (eg, heart disease, diabetes, hypertension) | |
| was not satisfied | | |
| Entered study even | History of frequent or recent severe, life-threatening episode of | 1 |
| though entry criteria | anaphylaxis or anaphylactic shock as defined by more than 3 | |
| was not satisfied | episodes of anaphylaxis | |
| Entered study even | History of eosinophilic GI disease | |
| though entry criteria | | |
| was not satisfied | | |
| Entered study even | Current participation or participation within 6 months prior to | |
| though entry criteria | screening in any other interventional study | |
| was not satisfied | servening in any other interventional study | |
| was not satisfied | | |

| Category | Description of Protocol Deviation | Notes |
|-----------------------|---|-------|
| Entered study even | Severe unstable asthma at time of enrollment with FEV1 <80% of | |
| though entry criteria | predicted, ACQ >1.5 or missing value (Original protocol and | |
| was not satisfied | accessed at visit 1) | |
| Entered study even | Use of systemic corticosteroids within 2 months prior to screening | |
| though entry criteria | | |
| was not satisfied | | |
| Entered study even | Use of omalizumab within 6 months prior to screening | |
| though entry criteria | | |
| was not satisfied | | |
| Entered study even | Use of other forms of allergen immunotherapy or | |
| though entry criteria | immunomodulatory therapy within 3 months prior to screening | |
| was not satisfied | | |
| Entered study even | Use of any agents known or likely to interact with epinephrine | |
| though entry criteria | within 3 weeks prior to screening | |
| was not satisfied | | |
| Entered study even | Allergy to oat (placebo in DBPCFC) | |
| though entry criteria | | |
| was not satisfied | | |
| Entered study even | Hypersensitivity to epinephrine and any of the excipients in the | |
| though entry criteria | epinephrine product | |
| was not satisfied | | |
| Entered study even | History of a mast cell disorder, including mastocytosis, urticarial | |
| though entry criteria | pigmentosa, and hereditary or idiopathic angioedema | |
| was not satisfied | | |
| Entered study even | Treatment with a live (attenuated) vaccine within 3 months prior to | |
| though entry criteria | screening and during the study | |
| was not satisfied | | |
| Entered study even | Active chronic or acute infection requiring systemic treatment with | |
| though entry criteria | antibiotics, antivirals, antiparasitics, antiprotozoals, or antifungals | |
| was not satisfied | within 2 weeks prior to the baseline visit | |
| | | |
| Entered study even | History of malignancy within 5 years before the screening visit | |
| though entry criteria | | |
| was not satisfied | | |
| Entered study even | Established diagnosis of a primary immunodeficiency disorder or | |
| though entry criteria | secondary immunodeficiency | |
| was not satisfied | | |
| Entered study even | Known history of human immunodeficiency virus (HIV) infection | |
| though entry criteria | or HIV seropositivity at the screening visit | |
| was not satisfied | | |
| Entered study even | With an established diagnosis of hepatitis B viral infection at the | |
| though entry criteria | time of screening or is positive for hepatitis B surface antigen or | |
| was not satisfied | hepatitis B core antibody at the time of screening | |
| Entered study even | Body weight <=17 kg or missing for screening V1 | |
| though entry criteria | | |
| was not satisfied | | |

[figure not shown]
| Category | Description of Protocol Deviation | Notes |
|------------------------|--|-------|
| Entered study even | Pregnant or breastfeeding women, women planning to become | |
| though entry criteria | pregnant or breastfeed during the study | |
| was not satisfied | | |
| Entered study even | Girls at or beyond menarche who are not sexually abstinent and are | |
| though entry criteria | unwilling to practice highly effective contraception | |
| was not satisfied | | |
| Entered study even | Serum IgE to peanut of >=10 kUA/L and/or a SPT to peanut >=8 | |
| though entry criteria | mm compared to a negative control (after PA2) | |
| was not satisfied | | |
| Entered study even | Use of anti-histamines within 5 days prior to screening and within 5 | |
| though entry criteria | days prior to SPTs and day 1 of DBPCFCs (SCR only) | |
| was not satisfied | days prior to Sr rs and day r or DDr or es (Sert only) | |
| Entered study even | Asthma at time of enrollment with any of the following: | |
| though entry criteria | FEV1<80% or predicted, or ratio of FEV1 to forced vital capacity | |
| was not satisfied | | |
| | (FEV1/FVC) <75% of predicted (PA1 and after) | |
| Entered study even | Asthma at time of enrollment with inhaled corticosteroids dosing of | |
| though entry criteria | > 500 ug daily fluticasone. (PA1 and after) | |
| was not satisfied | | |
| Entered study even | Asthma at time of enrollment with one hospitalization in the past | |
| though entry criteria | year for asthma or Emergency room visit for asthma within 6 | |
| was not satisfied | months prior to screening. (PA1 and after) | |
| Inadequate Informed | Subject did not sign an ICF (main study, pharmacogenomics, | |
| Consent administration | photography, imaging, etc) and study procedures initiated (never | |
| | signed ICF or signed after procedure) | |
| Inadequate Informed | Sub-study laboratory sample was collected without signed sub- | |
| Consent administration | study consent | |
| Inadequate Informed | Subject did not sign an amended ICF and study procedures initiated | |
| Consent administration | | |
| Inadequate Informed | Subject confidentiality not maintained | |
| Consent administration | | |
| Inadequate Informed | ICF is not in subject's language | |
| Consent administration | , | |
| Inadequate Informed | Study Procedures performed after patient withdraws full consent | |
| Consent administration | | |
| Other Treatment | Subject poor treatment compliance to SC study drug (define as | |
| compliance | underdose of 80% of planned doses overall) that significantly | |
| compliance | impacts efficacy outcome | |
| Other Treatment | Subject poor treatment compliance to SC study drug (define as | |
| compliance | overdose of 110% of planned doses) that significantly impacts | |
| compliance | efficacy outcome | |
| Other Treatment | Subject poor treatment compliance to AR101 study drug (define as | |
| | | |
| compliance | underdose of 95% of cumulative planned doses) that significantly | |
| Other Treatment | impacts efficacy outcome during updosing phase | |
| Other Treatment | Subject poor treatment compliance to AR101 study drug (define as | |
| compliance | underdose of 90% of cumulative planned doses) that significantly | |
| 01 T | impacts efficacy outcome during maintenance phase | |
| Other Treatment | Site staff were unblinded to the food challenge exposure | |
| compliance | (oat/peanut days) at DBPCFC at visit V16, V22 or V25. | |

| Category | Description of Protocol Deviation | Notes |
|-----------------------|---|-------|
| Procedure not | Demographics were not collected at Screening V1 | |
| performed | | |
| Procedure not | Vital Signs were not collected at Screening V1, V1A, V16, V22, | |
| performed | V25 | |
| Procedure not | Physical Examination was not collected at Screening V1 | |
| performed | | |
| Procedure not | Pregnancy Test (serum) was not collected at Screening V1 for | |
| performed | WOCBP. | |
| Procedure not | Peanut sIgE was not collected at Screening V1 | |
| performed | | |
| Procedure not | Spirometry was not collected at Screening V1a | |
| performed | | |
| Procedure not | Randomization was not collected at Baseline V2 | |
| performed | | |
| Procedure not | 2 or more Blinded Study Drug SC Q2W Administration was not | 1 |
| performed | collected at Baseline V2, V3, V4, V5, V6, V7, V8, V9, V10, V11, | |
| * | V12, V13, V14, V15, V16, V17, V18, V19, V20 or V21 (up to | |
| | PA2) | |
| Procedure not | Pregnancy Test (urine) was not collected at Baseline V2, V3, V4, | |
| performed | V5, V6, V7, V8, V9, V10, V11, V12, V13, V14, V15, V16, V17, | |
| 1 | V18, V19, V20, V21, V22 or Early Termination Visit for wOCBP | |
| Procedure not | Pregnancy Test (serum) was not collected at V25 EOS for WOCBP | |
| performed | | |
| Procedure not | Randomization was not collected at V16 | |
| performed | | |
| Procedure not | DBPCFC was not collected at V16 | |
| performed | | |
| Procedure not | DBPCFC was not collected at V22 | |
| performed | | |
| Procedure not | 2 or more Blinded Study Drug SC Q2W Administration was not | |
| performed | collected at Baseline V2, V3, V4, V5, V6, V7, V8, V9, V10, V11, | |
| | V12, V13, V14, V15, V15a, V15b, V15c, V15d, V15e, V15f, V16, | |
| | V17, V18, V19, V20 or V21 or in USCHED (PA3 and after) | |
| Procedure not | Pregnancy Test (urine) was not collected at V15a, V15b, V15c, | |
| performed | V15d, V15e, V15f for WOCBP (PA3) | |
| Procedure not | Weight was not collected at Baseline V2 | |
| performed | č | |
| Procedure performed | Food challenges were not performed either on different day, more | 1 |
| outside of window | than 1 day apart or less than 7-days apart during DBPCFC at on- | |
| | study visit V16, V22 or V25 EOS | |
| Randomization Error | Stratification error | 1 |
| Randomization Error | Subject randomized twice | |
| Received an excluded | | |
| concomitant treatment | Subject received prohibited medication impacting safety or efficacy parameters and assessments treatment with a live (attenuated) | |
| concommant treatment | vaccine per protocol | |
| Received an excluded | Treatment with an investigational drug (other than dupilumab) | - |
| concomitant treatment | (other than dupitumab) | |
| concommant treatment | | 1 |

| Category | Description of Protocol Deviation | Notes |
|-------------------------|--|-------|
| Received an excluded | Treatment with immunomodulating biologics agents, including | |
| concomitant treatment | anti-IgE and anti-IL-5 | |
| Received an excluded | Treatment with allergen immunotherapy other than AR101 | |
| concomitant treatment | | |
| Received an excluded | Treatment with systemic corticosteroids (up to PA1) | |
| concomitant treatment | | |
| Received an excluded | Treatment with any agents known or likely to interact with | |
| concomitant treatment | epinephrine (eg, betablockers, ACE-inhibitors, tri-cyclic | |
| | antidepressants, or other drugs) | |
| Received an excluded | Treatment with antihistamines within 5 days- prior to SPTs and | |
| concomitant treatment | Day 1 DBPCFCs (post randomization) | |
| Received an excluded | Major elective surgical procedures | |
| concomitant treatment | 5 6 1 | |
| Received an excluded | Treatment with systemic (oral, IV, IM, SC) corticosteroids for a | |
| concomitant treatment | duration of more than 5 continuous days, more than 15 days in | |
| | total, or within 2 days prior to DBPCFCs (PA2 and after) | |
| Received wrong | Subject given study drug but subject not randomized | |
| treatment or incorrect | , , , , , , , , , , , , , , , , , , , | |
| dose | | |
| Received wrong | Subject received incorrect treatment (wrong kit given, kit dispensed | |
| treatment or incorrect | without IVRS/IWRS transaction at re-supply visit, wrong order) | |
| dose | | |
| Received wrong | Subject received incorrect treatment or unacceptable IP (expired or | |
| treatment or incorrect | temperature excursion deemed unacceptable) that would impact | |
| dose | safety or efficacy | |
| Received wrong | Site level treatment unblinded (to for example Investigator, patient | |
| treatment or incorrect | or medical monitor) where patient care, decision making, data | |
| dose | analysis and reporting impacted | |
| Subject developed | | |
| withdrawal criteria but | Missing >2 consecutive doses of study drug (dupilumab or placebo) | |
| were not withdrawn | | |
| Subject developed | Missing >7 consecutive days of AR101 therapy (eg, concurrent | |
| withdrawal criteria but | illness such as gastroenteritis) | |
| were not withdrawn | | |
| Subject developed | Anaphylaxis resulting in severe hypotension (Appendix 3), | |
| withdrawal criteria but | neurological compromise, or mechanical ventilation secondary to | |
| were not withdrawn | OIT dosing or any food challenge. | |
| Subject developed | Subject develops biopsy-documented EoE or other eosinophilic GI | |
| withdrawal criteria but | disease | |
| were not withdrawn | | |
| Subject developed | Any subject deemed to have a severe allergic reaction or has a life- | |
| withdrawal criteria but | threatening reaction at any time but continues study treatment | |
| were not withdrawn | | |
| Subject developed | Other circumstances such as poor control or persistent secondary | |
| withdrawal criteria but | atopic disease or started beta blockers | |
| were not withdrawn | | |

| Category | Description of Protocol Deviation | Notes |
|-------------------------|--|-------|
| Subject developed | Any infection that is opportunistic, such as active tuberculosis and | |
| withdrawal criteria but | other infections whose nature or course may suggest an immuno- | |
| were not withdrawn | compromised status | |
| Subject developed | Severe laboratory abnormalities that are deemed to be related to | |
| withdrawal criteria but | dupilumab | |
| were not withdrawn | | |
| Subject developed | Diagnosis of a malignancy during the study | |
| withdrawal criteria but | | |
| were not withdrawn | | |
| Subject developed | Evidence of pregnancy | |
| withdrawal criteria but | | |
| were not withdrawn | | |
| Subject developed | Treatment with any prohibited concomitant medication or | |
| withdrawal criteria but | procedure but continued to take study drug | |
| were not withdrawn | Visit 16 was not norformed | |
| Visit not performed | Visit 16 was not performed | |
| Visit not performed | Week 52 Visit 22 (D365) was not performed | |
| Visit not performed | Week 64 Visit 25 EOS (D449) was not performed | |
| Visit not performed | Screening visit 1 (D-113 to D-17) was not performed | |
| Visit not performed | Screening visit 1A (D1 to D-15) was not performed | |
| Visit performed out of | Screening V1 (Day -57 to Day -17) was not performed -57 days of | |
| window | Baseline visit 2 (D1) (up to PA2) | |
| Visit performed out of | Visit 1A was not performed 15 days before visit 2 | |
| window | | |
